Title: Development and Evaluation of a Theory and Evidence-based Intervention to Reduce Hazardous Alcohol Consumption Among Treatment Seeking Smokers

NCT number: not yet assigned

Document date: October 20, 2025

Project background

We will measure the adoption of the alcohol resource in the patient portal by examining analytics data, which will be passively collected by the STOP patient portal. Given the evidence supporting the digital alcohol interventions that will be adapted for this population, and the larger sample that would be needed for an efficacy study, we will not directly evaluate the efficacy of the intervention in this study.

Specifically, we will test whether more eligible STOP patients accept the alcohol resource with the patient portal than did when it was offered by health care providers in the COMBAT, the cluster randomized control trial we conducted previously. In that study, 52.7% of participants scoring 8+ on the AUDIT-10 received an offer and 15.4% (95%CI = 13.9%, 17.1%) of the total sample (29% of those receiving an offer) accepted it. Reanalysis of COMBAT data showed that patient characteristics were minimally predictive of offer receipt and acceptance, while provider-level variance was substantial in both cases (ICCs \geq 0.50). This suggests that provider willingness to offer the intervention was the primary reason for the moderate offer proportion. In this study, we anticipate a similar acceptance rate, but will make the offer to all participants, yielding an anticipated acceptance rate of 29%.

Outcomes

Our primary outcome is **acceptance of the offered intervention**, defined as a response of 'yes' to the question, "Are you interested in receiving some information about alcohol and smoking and about ways of reducing alcohol use?"

Our secondary outcome is **continued participation in smoking cessation treatment**.

Analysis plan

Primary outcome: We will analyze the primary outcome using a chi-square test comparing the proportion in the present study to that in the original COMBAT project. We will use a significance level of 0.05 and will derive confidence intervals around both proportions and around the difference between them.

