Sensitivity analysis: To examine the potential sensitivity of this result to case-mix differences, we will use logistic regression to compare adoption in this sample to that among COMBAT participants with AUDIT scores of 8 or higher. Due to the small size of the sample in the current study, we will use propensity score weighting to adjust for age, gender, heaviness of smoking, AUDIT scores, education, income, and comorbid conditions. To account for sporadic missingness in these variables, we will use multiple imputation, with the number of imputed datasets dependent on the observed level of missingness.

Secondary outcome: For our secondary outcome, we will compare the proportion of participants who do not attend a clinical visit after self-enrolling to that among people self-enrolling before the study began who would have met study criteria. We will not examine longer-term retention due to the study timeline and the expectation that effects would be visible at the first contact.

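### The before/after comparison of first-visit non-attendance has no case-mix adjustment beyond matching on enrolment route and eligibility

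*SAP*

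**What the plan says.** The Outcomes section names the secondary outcome as "continued participation in smoking cessation treatment". The Secondary outcome paragraph of the Analysis plan makes this operational: "we will compare the proportion of participants who do not attend a clinical visit after self-enrolling", set against the same proportion among "people self-enrolling before the study began who would have met study criteria". No weighting, matching or covariate adjustment is named for this contrast. The paragraph also limits the time horizon: "We will not examine longer-term retention due to the study timeline and the expectation that effects would be visible at the first contact".

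The preceding Sensitivity analysis paragraph does deal with case mix. Its stated purpose is "To examine the potential sensitivity of this result to case-mix differences", and its content is to "compare adoption in this sample to that among COMBAT participants with AUDIT scores of 8 or higher". The method is given as "Due to the small size of the sample in the current study, we will use propensity score weighting", the covariates are "age, gender, heaviness of smoking, AUDIT scores, education, income, and comorbid conditions", and sporadic missing values are to be multiply imputed.

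**The concern.** The SAP contains two historical comparisons. It recognises case mix as a threat to the first (acceptance against COMBAT) and plans an analysis to probe it. The second (first-visit non-attendance, before against during the study) has the same non-randomised structure but no such analysis, and no reason is given for the difference.

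Restricting earlier self-enrollees to those who would have met the study criteria aligns the route into treatment and the entry rules. It does not balance the distribution of characteristics among eligible people. If people enrolling during the study smoke more heavily or have more comorbidity than those enrolling before, first-visit attendance could differ for that reason alone.

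The SAP expects to see effects at first contact, so it intends to read a difference causally. Longer-term retention is excluded, which leaves this single comparison as all the SAP offers on continued participation.

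**Working it through.** **Reading of the text**

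| | Sensitivity analysis | Secondary outcome |
|---|---|---|
| Outcome | Adoption of the alcohol resource | Non-attendance at a clinical visit after self-enrolling |
| Comparator | COMBAT participants, AUDIT 8 or higher | Earlier self-enrollees meeting study criteria |
| Restriction | AUDIT score | Self-enrolment and study eligibility |
| Further adjustment | Propensity weighting on seven covariates | None stated |

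The result to which the sensitivity analysis refers is the primary chi-square result directly before it. Both the outcome and the comparator differ from those of the secondary analysis, and the secondary paragraph, which comes afterwards, does not refer back. The case-mix analysis therefore does not reach the secondary outcome.

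**Size.** The SAP gives no sample size, rate or covariate distribution for this outcome, so there is no stated figure to reproduce. Every input below is an assumption.

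*Step 1: bias from one unbalanced binary covariate.* Bias = (difference in prevalence between periods) × (risk difference in non-attendance due to the covariate).

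- 0.05 × 0.10 = 0.005 (0.5 points)
- 0.05 × 0.20 or 0.10 × 0.10 = 0.01 (1 point)
- 0.10 × 0.20 = 0.02 (2 points)
- 0.20 × 0.20 = 0.04 (4 points)

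*Step 2: false-positive rate.* Assume n1 = 200 in the study, n0 = 600 earlier, earlier non-attendance p0 = 0.40, no true effect, and p1 = p0 + bias.

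SE = √[p1(1−p1)/n1 + p0(1−p0)/n0]

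P(reject) = 1 − Φ(1.96 − bias/SE) + Φ(−1.96 − bias/SE)

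For a 4-point bias: SE = √(0.2464/200 + 0.24/600) = 0.0404 and bias/SE = 0.99, so P(reject) = 1 − Φ(0.97) + Φ(−2.95) = 16.8%.

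| Bias (points) | Rejection rate of a nominal two-sided 5% test |
|---|---|
| 0.5 | 5.2% |
| 1 | 5.7% |
| 2 | 7.9% |
| 4 | 16.8% |

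The last figure moves slightly with the direction of bias and the variance formula, so about 17% is a fair summary. The 95% CI half-width is about 7.9 points.

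The result also depends on sample size. With equal groups, 30% non-attendance and a pooled test, a 2-point bias gives 6.1% (100 per group) or 7.2% (200 per group). A 4-point bias gives 9.3% or 13.7%.

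*Step 3: precision cost of weighting.* Suppose earlier enrollees are weighted to the study sample, study participants keep weight 1, and a single normal covariate is shifted by D standard deviations. The effective size of the earlier group is n0 × exp(−D²): 96% of n0 at D = 0.2 and 78% at D = 0.5. With k = n0/n1,

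SE ratio = √[(1 + exp(D²)/k) / (1 + 1/k)]

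| k | D = 0.2 | D = 0.5 |
|---|---|---|
| 3 (as in 200 against 600) | 1.005 | 1.035 |
| 1 (equal groups) | 1.010 | 1.069 |

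The standard error thus rises by 0.5% to 3.5% at k = 3 and by 1.0% to 6.9% at k = 1. Weighting on several covariates with larger joint shifts would cost more.

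**The case against.** The strongest reply is that the asymmetry is reasonable. COMBAT was a separate trial in which providers made the offer, whereas the earlier self-enrollees came through the same route and are restricted to study eligibility in the main analysis itself. The secondary comparator is closer, so case mix is less of a threat. That is fair and keeps the point small. But the SAP does not treat restriction as enough elsewhere: its sensitivity analysis restricts COMBAT to AUDIT 8 or higher and still weights on AUDIT score and six other factors.

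Second, the magnitude rests wholly on assumptions. The upper figure needs a 20-point prevalence shift together with a 20-point effect on non-attendance, which nothing in the SAP suggests, and every illustrated bias is smaller than the CI half-width. This stands: the calculation shows what could happen, not what is likely.

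Third, the fix may be only partly feasible. The SAP does not say which covariates are held for earlier enrollees; applying the study criteria implies that some baseline data exist, but not necessarily education, income or comorbidity. Nor can weighting touch calendar-time change. Both limits stand and must be stated with the result.

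Two other defences fail. The finding that patient characteristics predicted little in COMBAT concerns offer receipt and acceptance, not visit attendance, and the SAP adjusts the acceptance comparison regardless. The disclaimer of efficacy concerns the alcohol intervention; the SAP still expects effects on attendance.

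**Conclusion.** The concern holds. As written, the secondary outcome is a historical comparison with no case-mix control beyond enrolment route and eligibility, and the planned case-mix analysis does not cover it. A difference could partly reflect who enrolled in each period rather than the alcohol offer.

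The true bias cannot be computed from the SAP. Under the assumed inputs it ranges from negligible (0.5 points, 5.2% rejection) to material (4 points, about 17% rejection). That range assumes one binary covariate, 200 against 600 people, 40% non-attendance and no true effect. The point affects the interpretation of one secondary outcome and leaves the primary analysis untouched, so it is a worthwhile refinement rather than a serious defect.

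**What to change.** Keep the unadjusted comparison and report it as a risk difference with a 95% CI. Add one sensitivity analysis to the Secondary outcome paragraph:

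- Weight earlier eligible self-enrollees to the study sample by propensity score, with study participants keeping weight 1.
- Use those of the seven listed covariates that are held for both groups.
- Apply multiple imputation to sporadic missingness only, and leave out any covariate absent for all earlier enrollees.
- Report the weighted risk difference with a 95% CI, and covariate balance before and after weighting.
- State that weighting cannot remove secular change between the periods.

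The cost is a few lines of SAP text, a little more analysis work that reuses the planned weighting and imputation code, and some precision, lost on the earlier group because study participants are not reweighted. Adjustment may be partial if few covariates are available. Specifying it now avoids choosing an adjustment after the attendance results are known.
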